### 1.3.2. Rationale for the Study Design

Psoriatic arthritis may vary from a mild nonprogressive oligoarthritis to severe polyarticular disease, with great disability and reduced quality of life. These diverse clinical manifestations undermine general predictions regarding outcomes. Although PsA has been historically conceived as a more benign arthropathy, in some patients it follows a particularly aggressive and deforming course. Hence, early diagnosis and treatment may have a significant beneficial effect on the natural course of this disease.

This study is designed to determine the impact of apremilast on imaging outcomes, assessed by both MRI of the most affected hand and WB-MRI, in biologic-naïve subjects with active PsA, with  $\geq 3$  months and  $\leq 5$  years of disease duration, who had inadequate response to 2 or less csDMARDs. The purpose of the single-arm design of this trial is to obtain preliminary evidence of the impact of apremilast on MRI outcomes and structural progression of the disease.

Approved

A placebo-controlled study was not deemed necessary since current evidence in the literature shows that inflammation, as assessed by MRI, is not expected to significantly improve without an intervention in PsA. Moreover, a comparison arm with methotrexate was not pursued as the efficacy of MTX in PsA has not been convincingly proven in a randomized placebo-controlled trial.

### **1.3.3. Rationale for Dose, Schedule and Regimen Selection**

[figure not shown]
After a dose titration over a 5-day period, an oral dose of apremilast 30 mg BID will be given to all subjects. This is the approved dosing regimen of apremilast for the treatment of PsA.

In the Phase 3 PsA studies, a statistically significantly greater proportion of subjects in the apremilast 30 mg BID treatment group achieved the primary endpoint of ACR 20 response at Week 16 versus placebo. The statistically significant ACR 20 responses observed at Week 16 were maintained at Week 24 in the APR 30 BID group in all 3 pivotal studies. Therefore, the 24-week treatment period with frequent visits and assessments will provide adequate time to reasonably assess the effect of apremilast on clinical parameters and subject-reported outcomes, but especially on inflammatory and bony lesions classically associated with PsA, as assessed by MRI. This is also consistent with the design of clinical trials that evaluated the effect of biologic drugs in subjects with PsA through MRI assessments that have selected their primary endpoints at Week 24 in order to assess efficacy. The long-term effects of apremilast will be evaluated at Week 48. Indeed, results from the above-mentioned studies indicate that a longer follow-up is needed to detect changes in erosions with MRI.

Approved

## 2. STUDY OBJECTIVES AND ENDPOINTS

**Table 11: Study Objectives**

Primary Objective
The primary objective of the study is to evaluate the efficacy of apremilast 30 mg twice a day (BID) on inflammation indices, assessed by magnetic resonance imaging (MRI) of the hand.
Secondary Objective(s)

The secondary objectives of the study are to evaluate:
 

• The efficacy of apremilast 30 mg BID on imaging outcomes associated with structural progression, assessed by MRI of the hand.

• The efficacy of apremilast 30 mg BID on disease activity and functionality, assessed by clinical outcomes

• The efficacy of apremilast 30 mg BID on inflammation indices of peripheral arthritis and enthesitis, total (sum of arthritis and enthesitis) and separately, assessed by whole-body MRI (WB-MRI)

• The efficacy of apremilast 30 mg BID on The European League Against Rheumatism Psoriatic Arthritis Impact of Disease 12 domains (PsAID-12)

• The safety and tolerability of apremilast 30 mg BID

Exploratory Objective(s)
 A large rectangular area of the page is completely blacked out, indicating that the content has been redacted for confidentiality.

**Table 12: Study Endpoints**

Endpoint	Name	Description	Time Frame
Primary	Psoriatic Arthritis Magnetic Resonance Imaging Score (PsAMRIS) Inflammation Score of bone marrow edema [BME] + synovitis + tenosynovitis	Change from baseline in the composite score of BME, synovitis, and tenosynovitis assessed by PsAMRIS	Week 24
Secondary	Efficacy		
	PsAMRIS Inflammation Score of BME + Synovitis + Tenosynovitis	Change from baseline in the composite score of BME, synovitis, and tenosynovitis assessed by PsAMRIS	Week 48
	PsAMRIS BME + Synovitis	Change from baseline in the composite score of BME and synovitis assessed by PsAMRIS	Week 24 Week 48
	PsAMRIS Total Inflammation Score (BME + Synovitis + Tenosynovitis + Periarticular Inflammation)	Change from baseline in the PsAMRIS total inflammation score	Week 24 Week 48
	PsAMRIS BME	Change from baseline in BME assessed by PsAMRIS	Week 24 Week 48
	PsAMRIS Synovitis	Change from baseline in synovitis assessed by PsAMRIS	Week 24 Week 48
	PsAMRIS Tenosynovitis	Change from baseline in tenosynovitis assessed by PsAMRIS	Week 24 Week 48
	PsAMRIS Periarticular Inflammation	Change from baseline in periarticular inflammation assessed by PsAMRIS	Week 24 Week 48
	PsAMRIS Total Damage Score (erosion + bone proliferation)	Change from baseline in the PsAMRIS total damage score (erosion + bone proliferation)	Week 24 Week 48
	PsAMRIS Erosion	Change from baseline in bone erosion assessed by PsAMRIS	Week 24 Week 48
	PsAMRIS Bone Proliferation	Change from baseline in bone proliferation/enthesophytes assessed by PsAMRIS	Week 24 Week 48
	Swollen Joint Count (SJC)	Change from baseline in the SJC	Week 24 Week 48
	Tender Joint Count (TJC)	Change from baseline in the TJC	Week 24 Week 48

**Table 12: Study Endpoints (Continued)**

Endpoint	Name	Description	Time Frame
	Clinical Disease Activity Index for Psoriatic Arthritis (c-DAPSA)	Change from baseline in the c-DAPSA Score	Week 24 Week 48
	Spondyloarthritis Research Consortium of Canada (SPARCC)	Change from baseline in SPARCC, in subjects with preexisting enthesopathy	Week 24 Week 48
	Leeds Enthesitis Index (LEI)	Change from baseline in the LEI, in subjects with preexisting enthesopathy	Week 24 Week 48
	Enthesitis improvement to 0	Proportion of subjects with baseline enthesitis whose enthesitis improves to 0	Week 24 Week 48
	Leeds Dactylitis Index (LDI)	Change from baseline in the LDI, in subjects with preexisting dactylitis	Week 24 Week 48
	Dactylitis improvement to 0	Proportion of subjects with baseline dactylitis whose tender dactylitis count improves to 0	Week 24 Week 48
	Psoriatic Arthritis Disease Activity Score (PASDAS)	Change from baseline in the PASDAS	Week 24 Week 48
	Evaluator's Global Assessment of Disease Activity	Change from baseline in the evaluator's global assessment of disease activity	Week 24 Week 48
	Subject's Global Assessment of Disease Activity	Change from baseline in the subject's global assessment of disease activity	Week 24 Week 48
	Subject's Assessment of Pain	Change from baseline in the subject's assessment of pain	Week 24 Week 48
	Health Assessment Questionnaire-Disability Index (HAQ-DI)	Change from baseline in physical function (HAQ-DI score)	Week 24 Week 48
	WB-MRI Peripheral Enthesitis Inflammation Index	Change from baseline in the peripheral enthesitis inflammation index assessed by WB-MRI	Week 24 Week 48
	WB-MRI Peripheral Joints Inflammation Index	Change from baseline in peripheral joints inflammation index assessed by WB-MRI	Week 24 Week 48
	WB-MRI Total Peripheral Inflammation Index	Change from baseline in the total peripheral (joints and enthesitis) inflammation index assessed by WB-MRI	Week 24 Week 48

**Table 12: Study Endpoints (Continued)**

Endpoint	Name	Description	Time Frame
	BASDAI	Change from baseline in the BASDAI (for subjects deemed to have PsA spondylitis by the investigator and with BASDAI item 2 $\geq$ 4 at baseline)	Week 24 Week 48
	The European League Against Rheumatism Psoriatic Arthritis Impact of Disease 12 domains (PsAID-12)	Change from baseline in the PsAID-12	Week 24 Week 48
	Safety		
	The following parameters will be evaluated throughout the duration of the study:		
	Adverse events (AEs)	Type, frequency, severity and relationship of AEs to study medication	-
	Discontinuation due to AEs	Number of subjects who discontinue study medication due to any AE	-
	Clinically significant changes in physical examination, vital signs, and/or laboratory findings	Frequency of clinically significant changes in physical examination, vital signs, and/or laboratory findings	-
Exploratory			

Approved

**Table 12: Study Endpoints (Continued)**

Endpoint	Name	Description	Time Frame

Approved

**Table 12: Study Endpoints (Continued)**

Endpoint	Name	Description	Time Frame

Approved

### 3. OVERALL STUDY DESIGN

#### 3.1. Study Design

[figure not shown]
The study will be conducted in compliance with the International Council on Harmonisation (ICH) of Technical Requirements for Registration of Pharmaceuticals for Human Use/Good Clinical Practice (GCP) and applicable regulatory requirements. For all regions, the local Regulatory Label must be followed.

This is a Phase 4, multicenter, single-arm, open-label study to evaluate the impact of apremilast, either in monotherapy or with stable MTX, on MRI outcomes in subjects with active PsA with up to 5 years of disease duration (since diagnosis).

Approximately 120 subjects will receive apremilast 30 mg BID, after a 5-day titration period, with or without stable MTX. All subjects will be permitted to take NSAIDs and/or low-dose oral glucocorticoids (prednisone  $\leq$  10 mg/day or equivalent) throughout the study. The NSAIDs and low-dose oral glucocorticoids must be on a stable regimen for at least 4 weeks prior to baseline. MTX ( $\leq$  25 mg/week) will be permitted if treatment duration is  $\geq$  6 months and on a stable regimen for at least 3 months prior to baseline. In addition, the stable doses of MTX, NSAIDs, and low-dose glucocorticoids must be continued from Day 1 through the Week 24 Visit. Change in doses, increase or decrease, and/or discontinuation will not be allowed, except for safety reasons or for lack of availability. After the Week 24 Visit, the doses of MTX, NSAIDs, or glucocorticoids may be adjusted as clinically required.

[figure not shown]
This is a 56-week study which will consist of 3 phases, as shown in [Figure 1](#):

- Screening Phase – up to 4 weeks
- Single-arm, Open-label Treatment Phase – Weeks 0 to 48
  - 120 subjects will receive apremilast 30 mg BID (after a 5-day titration period) for the entire duration of this phase

- All subjects who complete the study or discontinue early will participate in the 4-week Post-treatment Observational Follow-up Phase. Henceforth, this will be referred to as the Observational Follow-up Phase.

**Figure 1: Overall Study Design**

BID = twice daily; MTX = methotrexate; Wk = Week.

Approved

### **3.2. Study Duration for Subjects**

Subjects who complete the study will spend up to a total of 56 weeks in this study:

- Up to 4 weeks in the Screening Phase
- Weeks 0 to 48 (ie, 48 weeks) in the Open-label, Single-arm, Treatment Phase
- 4 weeks in the Observational Follow-up Phase

### **3.3. End of Trial**

The End of Trial is defined as either the date of the last visit of the last subject to complete the post-treatment follow-up, or the date of receipt of the last data point from the last subject that is required for primary, secondary and/or exploratory analysis, as prespecified in the protocol, whichever is the later date.

Study completion is defined as the date of the last visit of the last subject in this clinical study. Study completion for an individual subject is defined as reaching Visit 7/48 weeks of treatment, and finishing the Observational Follow-up Visit at Week 52. A subject not meeting this definition is considered under early discontinuation (see Section 6.3). For the purpose of analyses, study completion for an individual subject is defined as reaching the Week 48 Visit.

Approved

## 4. STUDY POPULATION

Subjects must meet all inclusion criteria (Section 4.3) and must not have any of the conditions specified in the exclusion criteria (Section 4.4) to qualify for participation in the study. The subject's source documents must support his/her qualifications for the study (eg, if a female subject does not require pregnancy testing and birth control because of a hysterectomy, the date of the hysterectomy must be included in the medical history).

### 4.1. Medical and Disease History

Relevant medical history should be recorded, including smoking and alcohol history, as well as previous relevant surgeries. Disease history should include history of psoriasis and PsA.

### 4.2. Number of Subjects

Approximately 120 subjects will be enrolled worldwide.

### 4.3. Inclusion Criteria

Subjects must satisfy the following criteria to be enrolled in the study:

1. Males or females, aged  $\geq 18$  years at time of consent
2. For all regions, the local Regulatory Label for treatment with apremilast must be followed. For example, subjects in the EU must have had inadequate response or intolerance to a prior csDMARD.
3. Must understand and voluntarily sign an informed consent document prior to any study related assessments/procedures being conducted
4. Able to adhere to the study visit schedule and other protocol requirements
5. Have a documented diagnosis of PsA of  $\geq 3$  months AND  $\leq 5$  years in duration, meeting the CASPAR criteria for PsA ([Appendix B, Taylor, 2006](#)) at the time of Screening Visit
6. Have  $\geq 3$  swollen AND  $\geq 3$  tender joints, with hand involvement (defined as  $\geq 1$  swollen joint or dactylitis [each clinically active joint of a dactylitic digit is counted as one joint]).
7. Have at least 1 active enthesitis site (one of the SPARCC or LEI sites)
8. Must not have been treated previously with a TNF blocker or other biologic drug for PsA treatment
9. Must not have been treated with more than 2 csDMARDs
10. Subjects taking csDMARDs, with the exception of MTX, cyclosporine, or LEF (see Section 4.4, Exclusion Criterion 18, 19 and 20), do not require a washout period. However, they must discontinue the csDMARD treatment at least one day prior to their Baseline Visit (ie, Visit 2, Day 1)
11. Subjects who have been previously treated with MTX for  $< 6$  months and who are not on stable doses for at least 3 months will require a 28-day washout prior to the Baseline Visit (ie, Visit 2, Day 1) to participate in the study

12. Subjects who have been previously treated with LEF will require a 12-week washout prior to the Baseline Visit (ie, Visit 2, Day 1), or treatment with cholestyramine, per LEF prescribing label (ie, 8 g cholestyramine 3 times daily for 11 days)
13. Subjects who have been previously treated with cyclosporine will require a 28-day washout prior to the Baseline Visit (ie, Visit 2, Day 1) to participate in the study
14. If taking MTX ( $\leq 25$  mg/week), continuity of treatment will be allowed if duration of treatment is  $\geq 6$  months and on a stable dose for at least 3 months prior to the Baseline Visit (ie, Visit 2, Day 1)
15. If taking oral glucocorticoids, must be on a stable dose of prednisone  $\leq 10$  mg/day or equivalent for at least 4 weeks prior to the Baseline Visit (ie, Visit 2, Day 1)
16. If taking NSAIDs or narcotic analgesics, must be on stable dose for at least 4 weeks prior to Baseline Visit (ie, Visit 2, Day 1)
17. A female of childbearing potential (FCBP)† must have a negative pregnancy test at screening and baseline. While on IP and for at least 28 days after taking the last dose of IP, a FCBP who engages in activity in which conception is possible must use one of the approved contraceptive§ options described below:

Option 1: Any one of the following highly effective methods: hormonal contraception (oral, injection, implant, transdermal patch, vaginal ring); intrauterine device; tubal ligation; or partner's vasectomy;

OR

Option 2: Male or female condom (latex condom or non-latex condom NOT made out of natural [animal] membrane [for example, polyurethane]); PLUS one additional barrier method: (a) diaphragm with spermicide; (b) cervical cap with spermicide; or (c) contraceptive sponge with spermicide.

Note: Option 2 may not be acceptable as a highly effective contraception option in all countries, per local guidelines/recommendations.

† An FCBP is defined as a sexually mature female who 1) has not undergone a hysterectomy (the surgical removal of the uterus) or bilateral oophorectomy (the surgical removal of both ovaries) or 2) has not been postmenopausal for at least 24 consecutive months (that is, has had menses at any time during the preceding 24 consecutive months).

§ The female subject's chosen form of contraception must be effective by the time the female subject is screened into the study (for example, hormonal contraception should be initiated at least 28 days before screening).

18. Must be in general good health (except for PsA) as judged by the investigator, based on medical history, physical examination, and clinical laboratories. (Note: The definition of good health means a subject does not have uncontrolled significant comorbid conditions).

#### 4.4. Exclusion Criteria

The presence of any of the following will exclude a subject from enrollment:

1. Contraindication to MRI examination including, but not limited to, intracranial metal clips, heart pacemakers, insulin pumps, implanted hearing aids, neurostimulators, metal hip replacements, profound claustrophobia or inability to lie in the MRI machine in an

Approved

appropriate position to obtain quality images, history of hypersensitivity to gadolinium contrast agent

2. Severe renal impairment (creatinine clearance of less than 30 mL per minute estimated by the Cockroft–Gault equation), which would prevent the use of gadolinium enhancement
3. History of clinically significant (as determined by the investigator) cardiac, endocrine, pulmonary, neurologic, psychiatric, hepatic, renal, hematologic, immunologic disease, or other major uncontrolled disease
4. Any condition, including the presence of laboratory abnormalities, which places the subject at unacceptable risk if he/she were to participate in the study
5. Prior history of suicide attempt at any time in the subject's lifetime prior to signing the informed consent, or major psychiatric illness requiring hospitalization within the last 3 years prior to signing the informed consent.
6. Pregnant or breast feeding
7. Active substance abuse or a history of substance abuse within 6 months prior to screening
8. History of allergy or hypersensitivity to any component of the IP
9. History of rare hereditary problems of galactose intolerance, lapp lactase deficiency or glucose-galactose malabsorption
10. History of positive human immunodeficiency virus (HIV), or congenital or acquired immunodeficiency (eg, Common Variable Immunodeficiency Disease)
11. Active tuberculosis or a history of incompletely treated tuberculosis
12. Bacterial infections requiring treatment with oral or injectable antibiotics, or significant viral or fungal infections, within 4 weeks of screening. Any treatment for such infections must have been completed and the infection cured, at least 4 weeks prior to screening and no new or recurrent infections prior to the Baseline Visit
13. Malignancy or history of malignancy or myeloproliferative or lymphoproliferative disease within the past 3 years, except for treated (ie, cured) basal cell or squamous cell in situ skin carcinomas
14. Major surgery (including joint surgery) within 8 weeks prior to screening or planned major surgery within 6 months following Baseline Visit
15. Rheumatic autoimmune disease other than PsA, including, but not limited to: systemic lupus erythematosus, mixed connective tissue disease, scleroderma, polymyositis, or fibromyalgia
16. Prior history of or current inflammatory joint disease other than PsA (eg, gout, reactive arthritis, RA, ankylosing spondylitis, Lyme disease), which confounds the ability to interpret data from the study
17. Prior treatment with any biologic DMARD
18. Prior treatment with more than 2 csDMARDs

Approved

19. Use of the following systemic therapy(ies) within 28 days of the Baseline Visit (ie, Visit 2, Day 1): cyclosporine or other calcineurin inhibitors, glucocorticoids exceeding 10 mg daily prednisone equivalent, as well as mycophenolate
20. Use of MTX within 4 weeks of the Baseline Visit (ie, Visit 2, Day 1), unless subject is on stable doses for at least 3 months and total treatment duration with MTX is  $\geq$  6 months
21. Use of LEF within 12 weeks of the Baseline Visit (ie, Visit 2, Day 1), unless subject has taken cholestyramine, 8 g three times daily  $\times$  11 days after stopping LEF
22. Previous treatment with a JAK inhibitor (including tyk2 inhibitor)
23. Prior treatment with apremilast, or participation in a clinical study involving apremilast
24. Use of intra-articular (IA) glucocorticoid injection within 8 weeks before the Baseline Visit (ie, Visit 2, Day 1).
25. Use of any investigational drug within 4 weeks of the Baseline Visit, or 5 pharmacokinetic/pharmacodynamic half-lives, if known (whichever is longer)

Approved

## 5. TABLE OF EVENTS

Table 13: Table of Events

Visit Number	1 Screening	2 Baseline	3	4	5	6	7	Early Termination j  Assessments performed for Early Termination	Observational Follow-up  8 (or subsequent to Early Termination Visit)
	Week	Days -28 to 0	0	8 (+/-1 week)	16 (+/-1 week)	24 (+/-1 week)	36 (+/-1 week)		
Study Entry and General Assessments									
Informed Consent	X	-	-	-	-	-	-	-	-
Demographics	X	-	-	-	-	-	-	-	-
Medical History	X	-	-	-	-	-	-	-	-
Inclusion/Exclusion Criteria	X	X	-	-	-	-	-	-	-
Prior/concurrent Medications	X	X	X	X	X	X	X	X	X
Prior/concurrent Procedures	X	X	X	X	X	X	X	X	X
Biomarkers and Safety Assessments									
Vital Signs	X	X	X	X	X	X	X	X	-
Height	X	-	-	-	-	-	-	-	-

Approved

**Table 13: Table of Events (Continued)**

Visit Number	1 Screening	2 Baseline	3	4	5	6	7	Assessments performed for Early Termination	Early Termination j Observational Follow-up
	Days -28 to 0	0	8 (+/-1 week)	16 (+/-1 week)	24 (+/-1 week)	36 (+/-1 week)	48 (+/-1 week)		
Week								-	Week 52 or 4 weeks (+/-1 week) after Early Termination)
Weight	x	x	x	x	x	x	x	x	-
Assessment of Diarrhea	-	x	x	x	x	x	x	x	-
Complete Physical Exam a	x	-	-	-	x	-	x	x	-
Limited Physical Exam a	-	x	x	x	-	x	-	-	-
Complete Blood Count	x	x	x	x	x	x	x	x	-
Serum Chemistries	x	x	x	x	x	x	x	x	-
 									
Hemoglobin A1c	-	x	-	-	x	-	x	x	-
Urinalysis	x	x	-	-	x	-	x	x	-
Pregnancy Test c (FCBP only)	x	x	-	-	-	-	x	x	-
Contraception Education d	x	x	-	-	-	-	-	-	-
Adverse Events e	x	x	x	x	x	x	x	x	x
Efficacy Assessments									
Tender Joint Count (0-78)	x	x	x	x	x	x	x	x	-
Swollen Joint Count (0-76)	x	x	x	x	x	x	x	x	-
Subject Global Assessment of Disease Activity	x	x	x	x	x	x	x	x	-

Approved

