### **6.3. Observational Follow-up Period**

#### **6.3.1. Safety Follow-up**

All subjects will be followed for 28 days after the last dose of IP for AE reporting, as well as any SAEs made known to the Investigator at any time following the protocol-required reporting period or after end of study t, as described in Section 10.1. Safety assessments are specified in the Table of Events, [Table 13](#).

[figure not shown]

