All AEs will be recorded by the Investigator from the time the subject signs informed consent until 28 days after the last dose, as well as any SAEs made known to the Investigator at any time following the protocol-required reporting period or after end of study will also be reported for these subjects. All adverse events (serious/non-serious) will be recorded on the CRF, the paper SAE Report form (SAEs) and in the subject's source documents. All SAEs must be reported to Amgen Global Patient Safety within 24 hours of the Investigator's knowledge of the event by recording on the CRF and using the paper Serious Adverse Event Report Form by facsimile/email of the paper SAE Report Form directly to Amgen Global Patient Safety.

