## 11. DISCONTINUATIONS

### 11.1. Treatment Discontinuation

The following events are considered sufficient reasons for discontinuing a subject from the IP (apremilast):

- Adverse event(s)
- Lack of efficacy
- Non-compliance with study drug
- Withdrawal of consent
- Study termination by sponsor
- Lost to follow-up
- Pregnancy
- Death
- Protocol deviation
- Other (to be specified on the CRF)

Subjects have the right to withdraw from the study at any time and for any reason. The reason for discontinuation should be recorded in the CRF and in the source documents.

When a subject discontinues from treatment, the Investigator will make every attempt possible to have the subject evaluated at the Early Termination Visit within 4 days of the last intake of investigational product.

The decision to discontinue a subject from treatment can be taken at any time and remains the responsibility of the treating physician, which will not be delayed or refused by the Sponsor. However, prior to discontinuing a subject, the Investigator may contact the Medical Monitor and forward appropriate supporting documents for review and discussion.

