4.2.5.1. Treatment-Emergent Adverse Event

A treatment-emergent adverse event (TEAE) is defined as any AE that begins or worsens on or after the date of the first dose of investigational product (IP) and no later than 28 days after the

last dose of IP for subjects who have completed the study or have discontinued early by the time of database cut.

If the treatment-emergent status of an AE is unclear due to a missing/incomplete start date, it will always be considered treatment-emergent, unless shown otherwise by data. Date imputation rules for partially missing AE start dates are described in Appendix [A1 1.1](#).

4.2.5.2. Treatment-emergent Adverse Events Leading to Drug Withdrawal, Leading to Drug Interruption, and Leading to Death, and Drug-related Treatment-emergent Adverse Events

A TEAE leading to drug withdrawal is a TEAE for which the investigator indicates that the action taken with respect to IP is withdrawn permanently (action taken on AE eCRF is recorded as “DRUG WITHDRAWN”). A TEAE leading to drug interruption is a TEAE for which the investigator indicates that the action taken with respect to IP is drug interrupted. A TEAE leading to death is a TEAE for which the outcome is fatal. Relationship to IP is based on the investigator's causality judgment; that is, a drug-related AE is an AE indicated by the investigator to have a suspected relationship to IP.

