5.3. Analysis Periods

In this study, the analysis periods are divided into open label treatment period and observational follow-up period below.

- Open label treatment period – Week 0 to Week 48

This period starts on the day after the first IP is dispensed (Visit 2/Week 0), and stops on either: (1) the completion date of treatment period collected in the eCRF; or (2) the early termination date of treatment period collected in the eCRF; or (3) the last known study date if the subject is lost to follow-up.

- Observational follow-up period – 4 weeks

Subjects who complete the study or early terminate from the study, will be followed up for 28 days after the Visit 7/Week 48 or Early Termination visit. The period starts at the end date of treatment period + 1 and stops on either (1) the completion date of follow-up period in eCRF; (2) the last known study date if the subject is lost to follow-up.

For efficacy analysis, only the open-label treatment period will be used.

For safety analysis, the open-label treatment period and observational follow-up period will be included into the data summary.

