1.1 Adverse Events

The principle of the imputation rules for subjects who were treated with apremilast initially is to treat the AE as treatment-emergent, i.e., occurring on or after the date of the first dose of IP, if possible.

Partially missing AE start date will be imputed in the ADaM dataset for AEs, but partially missing AE end dates will not be imputed in the same dataset. If the AE end date is complete with no missing year, month, or day, and the partially missing start date imputed by the rules below is after the AE end date, then the start date will be imputed by the AE end date.

The following scenarios are considered in the imputation rules:

- If AE start day is missing, and AE start month and year are not missing:
 - If AE start year and month are the same as the year and month of first dose, then impute AE start day using the day of first dose date.
 - If AE start date is less than the first dose date, then impute AE start day using the last day of AE start month.
 - If AE start date is greater than the first dose date, then impute AE start day using the first day of AE start month.
- If both AE start month and day are missing, and AE start year is not missing:
 - If AE start year is less than the year of first dose, then impute AE start date using the last day of the AE start year.
 - If AE start year is equal to the year of first dose, then impute AE start date using the first dose date.
 - If AE start year is greater than the year of first dose, then impute AE start date using the first day of the AE start year.

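### Table 13 lets the only post-treatment AE contact fall before Day 28 after the last dose, and the SAP 5.3 analysis periods do not match the TEAE window at either end

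*Protocol*

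**What the plan says.** **Length of AE follow-up.** Protocol 6.3.1 states: "All subjects will be followed for 28 days after the last dose of IP for AE reporting". Protocol 10.1 sets the recording window as running "from the time the subject signs informed consent until 28 days after the last dose", and 6.5.8 agrees. SAP 4.2.5.1 gives the timing of a TEAE as follows: "begins or worsens on or after the date of the first dose of investigational product (IP) and no later than 28 days after the" (the sentence goes on to name the final IP intake).

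**Timing of the contact.** The Observational Follow-up column of Table 13 gives "Week 52 or 4 weeks (+/-1 week) after Early Termination". The Week 48 visit has its own tolerance of one week either way. Protocol 11.1 asks that the Early Termination (ET) visit take place "within 4 days of the last intake of investigational product". Table 13 shows no later contact, and Protocol 3.3 counts a subject as having completed the study once the Week 52 follow-up visit is done.

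**SAP analysis periods.** On the open-label treatment period, SAP 5.3 says: "This period starts on the day after the first IP is dispensed". The follow-up period is described as 28 days counted from Visit 7 or the ET visit, and it stops at "the completion date of follow-up period in eCRF" or, for a subject lost to follow-up, at the last known study date. Safety summaries use these two periods. SAP Appendix A1 1.1, for an AE with a missing start day in the month of first dose, says to "impute AE start day using the day of first dose date". A similar rule applies when only the year is known.

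**The concern.** The 28-day window is anchored on the last dose. The contact meant to close it is anchored on calendar Week 52 or on the ET visit, with a tolerance that allows it to be early. A site can therefore follow the schedule exactly and hold its last planned AE enquiry before the window has closed. A non-serious event that begins after that contact enters the database only if the subject reports it unprompted, so events soon after stopping treatment could be under-counted.

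The SAP has a related problem. Two of its definitions, the TEAE window and the safety analysis period, select different sets of events. The difference at the start matters because Appendix A1 deliberately places partly dated AEs on the first-dose date, and SAP 5.3 as worded begins the day after. Treatment duration in SAP 10.1 counts the first-dose date, so on the literal reading the exposure-adjusted rates would include a day in the denominator whose events are missing from the numerator.

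**Working it through.** **Inputs.** Week 48 is Day 336 (SAP Table 2), with a tolerance of ±7 days (Table 13), so Days 329 to 343. Week 52 = 52 × 7 = Day 364. ET follow-up is at 28 ± 7 days after the ET visit (Table 13). The ET visit is taken as 0 to 4 days after the last dose (Protocol 11.1). The required window is 28 days after the last dose.

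**The plan's own figure.** With both visits on target, (52 − 48) × 7 = 28 days. The nominal schedule reproduces the stated 28 days.

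**Earliest permitted contact.** Completers are assumed to take the last dose on the Week 48 visit date.

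| Case | Gap, last dose to contact | Shortfall against 28 days |
|---|---|---|
| Early terminator, ET visit on day of last dose | 28 − 7 + 0 = 21 | 7 days (7/28 = 25%) |
| Early terminator, ET visit 4 days after last dose | 28 − 7 + 4 = 25 | 3 days (3/28 = 11%) |
| Completer, Week 48 at +7, Week 52 without window | 364 − 343 = 21 | 7 days (25%) |
| Completer, Week 48 at +7, only if ±1 week applies to Week 52 | 357 − 343 = 14 | 14 days (14/28 = 50%) |

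If the completer's last dose is the day before the visit, one day is added: 22 and 15 days. The full range for completers is 21 to 35 days without a Week 52 window and 14 to 42 days with one, so many compliant visits fall on or after Day 28.

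**End of the SAP period against the TEAE window.** Take a completer seen at Day 343 and again at Day 364. The TEAE window ends at 343 + 28 = Day 371. If the eCRF completion date is the visit date, the SAP 5.3 period ends at Day 364, 7 days sooner. With the Week 48 visit at Day 329, the TEAE window ends at Day 357 and the period at Day 364, 7 days later. The mismatch therefore runs in both directions.

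**Start of the SAP period against the TEAE window.** SAP 10.1 puts the first dose at Visit 2/Week 0, which is the dispensing visit, and SAP 10.2 counts one dose on study Day 1. The TEAE window therefore opens on Day 1 and the SAP 5.3 period on Day 2, a difference of one day. The partly dated AEs that Appendix A1 assigns to the first-dose date fall on that day.

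**After the fix.** With the last contact no earlier than last dose + 28 days, and the period running from first dose to last dose + 28 days, the shortfall is 0 days at each end.

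**The case against.** The strongest reply is that neither the obligation nor the analysis depends on the visit date. Protocol 6.3.1, 6.5.8 and 10.1 require recording to Day 28 whenever the visit occurs, and SAEs that come to light later are reportable without time limit. SAP 5.3 itself describes 28 days of follow-up from Visit 7 or ET which, with treatment ending by that visit, would cover the window. AE tables are built on the TEAE definition, which explicitly includes the first-dose date.

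Much of this stands, and it rules out several stronger readings that a reader might infer:

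- *Events after an early visit are lost.* The documents do not say so. What is missing is a scheduled later contact, so the risk is confined to non-serious AEs that are not volunteered.
- *Half of the window goes unobserved.* That requires the ±1 week to apply to Week 52. In the column heading the tolerance follows the 4 weeks after ET. Protocol 3.3 gives Week 52 no window, and Protocol 3.1 and 3.2 describe a 4-week follow-up phase.
- *Pregnancies in the window are missed for the same reason.* Table 13 schedules no pregnancy test at the follow-up visit, the last being at the final treatment or ET visit. Moving the follow-up visit would add no test, and the reporting duty for pregnancies is separate.
- *Day 1 AEs will be dropped from the tables.* The date filter in SAP 5.5 assigns measured values to time points and does not select AE onsets. The loss follows only from a literal reading of SAP 5.3, whose wording is probably a slip.

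The reply does not remove two things. Table 13 still permits the last planned AE enquiry before Day 28. And the 28 days in SAP 5.3 are counted from a visit, with a stopping rule at an eCRF date, so they do not reproduce the limits in SAP 4.2.5.1.

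**Conclusion.** The inconsistency is real and modest. Compliant scheduling can put the last AE contact 21 to 25 days after the last dose for early terminators, and 21 days for completers with a Week 48 visit at +7 days. That leaves 3 to 7 of the 28 days without a planned enquiry. The 14-day, 50% figure is conditional on the wider reading of the Week 52 tolerance. These are earliest cases around a nominal 28 days, and the documents do not show how many subjects would be seen early.

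The figures assume the last dose is taken on the Week 48 visit date and the ET visit occurs 0 to 4 days after the last dose; a later ET visit shortens the gap in coverage. That the SAP period closes at the follow-up visit is inferred from the completion definition in Protocol 3.3, because SAP 5.3 names only an eCRF date.

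The one-day mismatch at the start of the period is certain as wording. Its effect on the tables is not, since programmers may simply follow SAP 4.2.5.1. A prespecified plan should not leave that choice open. No efficacy result is affected.

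**What to change.** 1. **Protocol Table 13 and 6.3.1.** Reconcile the passages so that the final AE contact, by visit or telephone, takes place no earlier than 28 days after the last dose. This uses the protocol's own limit and adds no new follow-up length. A subject seen sooner would be telephoned on or after Day 28. State explicitly whether Week 52 carries a window.
2. **SAP 5.3.** For AE summaries, define the period as the date of first dose through the date of last dose plus 28 days, as in SAP 4.2.5.1. This also brings the section into line with Appendix A1.

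The cost is a changed visit tolerance and one SAP sentence. Some follow-up visits move later, by up to 7 days, or up to 14 on the wider reading of Week 52; otherwise a short call is added. The SAP change has no operational cost.
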